6.1.2. Adjustments for Covariates

In addition to treatment group, the baseline value of the variable undergoing analysis and the co-medication type (Anticonvulsant versus Antidepressant) will be included in the analysis of covariance (ANCOVA) model as additive covariates. Co-medication type will be determined by blinded clinical review of each subject's medication record at baseline.

Covariates in the mixed effects models repeated measures (MMRM) and generalized estimating equations (GEE) analyses include those specified for the ANCOVA analyses, together with time and its interaction with dose group.

The crossing of co-medication type and median baseline pain score will be used as strata in the Cochran-Mantel-Haenszel (CMH) model tests. Assuming two co-medication types, the strata will be:

[figure not shown]
- 1) Anticonvulsant (Baseline NRS < Median),
- 2) Anticonvulsant (Baseline NRS > Median),
- 3) Antidepressant (Baseline NRS < Median),
- 4) Antidepressant (Baseline NRS > Median).

Where the median baseline NRS is calculated over all subjects.

6.1.3. Multiple Comparisons

A multiple comparison procedure modelling approach (MCP-Mod) on LOCF data will be used for primary efficacy endpoints.

AD-ST-33.06 Effective date: 12-Nov-2020

No adjustments will be made for multiple comparisons outside the MCP-Mod approach.

6.1.4. Handling of Dropouts or Missing Data

For the analyses of the primary efficacy endpoints based on the mITT Population, a variety of methods will be used to deal with missing data, including:

- Primary Method: LOCF.
- Observed cases analysis.
- Baseline observation carried forward (BOCF)

Subjects with missing weekly average NRS baseline data (i.e., zero or 1-3 days of diary pain scores) will not be included in the efficacy analysis because the primary analysis is change-from-baseline. If a subject has zero or ≤ 3 days of diary pain data in each of the possible post-baseline seven day periods ending within the protocol definition of week 12 (day 84 ± 3), then an imputed 'week 12 LOCF' weekly average NRS pain score will be calculated from the latest 7 'non-missing' entries of the subject's diary closest to their nominal week 12 visit (i.e., the latest 7 day period containing at least 4 NRS values), provided that this would qualify as at least 'week 2' according to the windowing outlined in Section 6.1.5. Otherwise, the week 12 LOCF weekly average NRS pain score will be set to missing.

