2.1.3. Exploratory Objectives

2.2. Study Endpoints

2.2.1. Efficacy Endpoints

2.2.1.1. Primary Efficacy Endpoint

The primary efficacy endpoint of this study is the change in the weekly average of the average daily pain scores from the baseline week to Week 12 of MEDI7352 compared to placebo, as measured on an 11-point (0-10) numeric rating scale (NRS).

The target population is the entire patient population, i.e., the collection of all patients eligible to be included in the randomized clinical trial based on prespecified (and duly justified) inclusion/exclusion criteria.

The study was not designed using the Estimand framework. However, the following general aspects of an Estimand can be inferred: the Estimand can be generically defined as the true between-treatment difference in the target population endpoint means for the change from baseline for the Pain NRS at Week 12, while-on-treatment and regardless of prohibited or rescue medication use.

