2.2.4. Other Endpoints

The following endpoints will be assessed:

- Change in the weekly average of the average daily pain scores from the baseline week to Week 12, as measured on an 11-point (0-10) NRS, versus dose.
- Immunogenicity (ADA) assessments.

3. Overall Study Design and Plan

This is a randomised, double-blind, placebo-controlled study of MEDI7352 in subjects with moderate to severe chronic PDN persistent for 6 months or longer, not adequately controlled by standard of care treatments, caused by type 1 or type 2 diabetes mellitus. The study incorporates a screening period of up to 45 days and a 12-week double-blind treatment period during which MEDI7352 or placebo will be administered intravenously (IV) on 6 occasions, with each dose separated by 14 days. There will be a 6-week follow-up period.

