3.4. Treatments Administered

Once randomized, subjects will be dosed with either MEDI7352 or placebo on Day 1, Day 14, Day 28, Day 42, Day 56, and Day 70. MEDI7352 or placebo will be administered IV over a 60-minute period. To maintain the blind, a placebo volume equivalent to the MEDI7352 volume will be administered for each dosing.

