6.1.5. Analysis Visit Windows

Statistical analyses will be based on scheduled visits and windows as per Protocol Table 2-1: Schedule of Events. If an assessment falls between 2 windows, then the closest visit will be used only if an assessment result is not provided within that window. All other visits will be listed only as unscheduled visits. For presentation purposes these will be mapped to the visit prior and labeled, e.g., Unscheduled Visit 3.1, if Visit 3 was the closest date prior.

For pain diary data the following analysis periods will be defined:

• Week X_i: the 7-day period ending within the protocol window Day Y_i±3 where at least 4 days out of 7 have recorded diary pain scores. Where several such windows exist the one ending closest to day Y_i will be selected. If there are two such windows that are equidistant from day Y_i, then the one with the largest number of diary entries will take precedence. If they have the same number of entries, then the later of the two end dates will be chosen. If no such window exists, then week X_i will be considered missing for the purposes of weekly average scoring.

Where:

• $X_1=2, Y_1=14$

• $X_2=4, Y_2=28$

• $X_3=6, Y_3=42$

AD-ST-33.06 Effective date: 12-Nov-2020

Version 1.1 | Date 31-Aug-2023 | AD-PR-109.02 Effective date: 17-Aug-2020

Page 20 of 54

- $X_4=8, Y_4=56$
- $X_5=10, Y_5=70$
- $X_6=12, Y_6=84$
- The week before follow-up is defined as the 7-day period prior to the last day of pain diary data for subjects completing the study (i.e., entering in the Week 18) where at least 4 days out of 7 have recorded diary pain scores.

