6.1.8. Derived Variables

- Change from baseline = value at current time point value at baseline.
- Reference End Date = Date of completion/discontinuation.
- Study duration = Reference end date date of first dose of treatment + 1
- Duration of exposure (days) = min(date of last dose of treatment + 14 days or date of death) date of first dose of treatment + 1.
- Treatment-emergent AEs (TEAEs) are defined as:
 - o AEs with onset at the time of or following the start of treatment with IP, or
 - AEs starting prior to the start of treatment but increasing in severity or relationship at the time of, or following, the start of treatment with IP.
- Average Baseline Pain NRS = the arithmetic average of the 'non-missing' daily pain scores within the baseline period defined in Section 6.1.1. For example, if a subject has 5 days of non-missing pain scores their average will be calculated over 5 days, not the full 7-day baseline period.
- Average Week X Pain NRS = the arithmetic average of the 'non-missing' daily pain scores within each subject's specific week X period defined in Section 6.1.5.
- Average Week 12 Pain NRS (LOCF) = the arithmetic average of the 'non-missing' daily pain scores within each subject's specific week 12 period or according to the imputed LOCF/BOCF approach defined in Section 6.1.4.
- Change from Baseline to Week X Pain NRS = for each subject 'Average Week X Pain NRS' minus 'Average Baseline Pain NRS'.
- Change from Baseline to Week 12 Pain NRS (LOCF/BOCF) = for each subject 'Average Week 12 Pain NRS (LOCF)' minus 'Average Baseline Pain NRS'.
- Galer NPS Total Score (ranges from 0 to 100): sum of Pain Intensity, Pain Unpleasantness, Pain Sharpness, Pain Hotness, Pain Dullness, Pain Coldness, Pain Sensitivity, Pain Itching, Deep Pain Intensity, and Surface Pain Intensity (All in an 11-point NRS).
- Change from Baseline to Week X Galer NPS Total Score = for each subject 'Galer NPS Total Score' minus 'Baseline Galer NPS Total Score'.
- Total number of days rescue medication was used = End Date of Medication Start Date

of medication + 1. Each day on which rescue medication was used at least once is counted.

- Cumulative consumption (mg) of paracetamol rescue medication use = Total dose of rescue medication (mg) consumed during the days in which paracetamol was used.

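### The Week 12 LOCF rule has no upper day limit, so a follow-up week can become the primary endpoint value; BOCF has no rule of its own

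*SAP*

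**What the plan says.** The rules are in SAP v1.1; v1.0 has the same text, and Section 6.1.2 of the interim analysis plan has nearly the same LOCF wording.

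- **Trigger and source of the LOCF value (Section 6.1.4).** If no 7-day period ending on Day 84 ± 3 has four diary scores, the Week 12 value comes from "the latest 7 'non-missing' entries of the subject's diary closest to their nominal week 12 visit (i.e., the latest 7 day period" that holds at least four scores.
- **Only bound (Section 6.1.4).** The period is accepted "provided that this would qualify as at least 'week 2' according to the windowing outlined in Section 6.1.5". No last day and no link to dosing is given.
- **Diary after treatment (Section 6.1.5).** "The week before follow-up is defined as the 7-day period prior to the last day of pain diary data for subjects completing the study", which the section ties to Week 18. Section 3 gives a 12-week treatment period followed by six weeks of follow-up.
- **Dosing and exposure.** Doses are given on "Day 1, Day 14, Day 28, Day 42, Day 56, and Day 70" (Section 3.4). Section 6.1.8 counts exposure to 14 days after the last dose.
- **Estimand (Section 2.2.1.1).** The treatment difference is described as "while-on-treatment and regardless of prohibited or rescue medication use".
- **BOCF.** Section 6.1.4 lists it as a method and says no more. Section 6.1.8 has: "Change from Baseline to Week 12 Pain NRS (LOCF/BOCF) = for each subject 'Average Week 12 Pain NRS (LOCF)' minus 'Average Baseline Pain NRS". The same section defines that LOCF-labelled average by an LOCF/BOCF approach said to be in Section 6.1.4. Table 14.2.1.3.2 is an MCP-Mod sensitivity analysis on BOCF data.

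**The concern.** This variable feeds the primary MCP-Mod test, so its derivation should give one value per subject, and that value should come from the period the estimand describes. As written, a pain score recorded up to eight weeks after the last dose (Day 126 − Day 70 = 56 days) can stand in for Week 12. Two programmers could follow the same sentence and produce different endpoints. If the ambiguity is settled only after unblinding, the choice is open to the charge of being driven by the data.

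BOCF is the only listed repeat of the MCP test itself under a different missing-data method. A BOCF table that reproduced LOCF would look like robustness without testing it.

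**Working it through.** **1. The plan's own figures.** The counts agree: 14 + 30 + 37 = 81 on placebo, 81 + 37 + 51 + 67 = 236 evaluable, 28 + 60 + 148 = 236, and 30 + 67 + 165 = 262 randomised. Power inputs from Section 3.2 are SD 2.4, difference 1.25, one-sided alpha 0.025 and candidate ED50s of 7.5, 15, 30, 60 and 750 µg/kg. The dose labels there are redacted. I assumed 0/50/150/450 from the table shells for group sizes 81/37/51/67. Optimal contrasts and a simulated multivariate t (236 − 4 = 232 df) give a critical value of 2.195. Power is 0.948 at a true ED50 of 1 and about 0.875 at 750. Two other dose sets (0/5/150/450 and 0/5/50/150) give about 0.90 to 0.95. As a rough check, top dose against placebo has SE = 2.4 × √(1/81 + 1/67) = 0.396, and 1.25/0.396 − 1.96 = 1.19, which is power of about 0.88. The statement of more than 80% is reproduced.

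**2. The LOCF rule applied to two example diaries.** Windows ending on Days 81 to 87 cover Days 75 to 87. Neither diary has an entry there, so both go to imputation.

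| Reading | A: entries Days 1–70 and 95–126 | B: entries Days 1–60 and 90–126 |
|---|---|---|
| Latest seven entries | Days 120–126 | Days 120–126 |
| Latest 7-day period with ≥4 scores, window allowed to run past the last entry | ends Day 129 (scores on Days 123–126) | ends Day 129 (scores on Days 123–126) |
| Period closest to Day 84 | ends Day 73 (11 days away) | ends Day 93 (9 days away) |
| Last period ending by Day 87 | ends Day 73 | ends Day 63 (21 days from Day 84) |

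Under *latest*, both subjects receive a follow-up week. Under *closest*, A does not but B does, because 93 − 84 = 9 is less than 84 − 63 = 21. So neither reading keeps follow-up data out. The first two rows also show that seven entries and a 7-day period with at least four scores need not average the same days: seven scores in one case, four in the other.

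**3. Size.** Let *f* be the share of subjects given a follow-up value and *r* the fraction of the effect still present then. Neither is in the document. With placebo follow-up pain assumed equal to its Week 12 level, the difference becomes 1.25 × (1 − f(1 − r)).

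- f = 5%, r = 0: 1.25 × 0.95 = 1.19.
- f = 10%, r = 0: 1.25 × 0.90 = 1.125.
- Any f with r = 1: no change.

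Power with r = 0, on the assumed doses (simulated):

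| True ED50 | f = 0 | f = 5% | f = 10% |
|---|---|---|---|
| 7.5 | 0.940 | 0.915 | 0.883 |
| 60 | 0.903 | 0.872 | 0.835 |
| 750 | 0.874 | 0.838 | 0.796 |

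The 10% ceiling borrows the plan's withdrawal rate and is likely too high for this group.

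**4. The BOCF definition traced.** The change formula in Section 6.1.8 uses the LOCF-labelled average. That average points to an LOCF/BOCF approach in Section 6.1.4, which contains only the LOCF algorithm. Followed literally, the BOCF change equals the LOCF change. For contrast, a BOCF that set 10% of each arm to zero change would move placebo from −1 to −0.9 and the top dose from −2.25 to −2.025, a difference of 1.125, if the remaining subjects keep the planned means.

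**The case against.** The context points to a narrower intention. The method's name implies carrying forward, and Section 3.2 describes it as being for withdrawn subjects. The LOCF summary shell stops at Week 12 while the observed-case shell runs to Week 18. The interim plan calls Day 87 the upper limit of the Week 12 window and builds its Week 6 LOCF set from Week 6 to 11 averages. The estimand is only inferred, for a study the SAP says was not designed in that framework. The affected subject must miss nearly all entries around Week 12 and then resume the diary, and Section 6.1.5 ties the follow-up diary week to completers. All of this supports what was probably meant and a small affected group. It does not supply the missing upper day, and the shells cannot override the algorithm.

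On BOCF, the objection is stronger. The shells ask for observed plus BOCF data, a separate MCP-Mod table, and boxplots of observed, LOCF and BOCF data side by side, so the authors meant it to differ. What stands is the absent rule and the mislabelled formula.

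A reader might also infer that BOCF is the only missing-data check of the primary endpoint. It is not: observed cases are a named method, and an MMRM on observed data at Weeks 2 to 12 is planned. Nor does the text say that subjects without a Week 2 average never enter. A valid later week satisfies the LOCF bound, and with no BOCF rule one cannot say whom BOCF excludes. The 26 of 262 randomised subjects allowed as non-evaluable (262 − 236) therefore cannot be equated with that group.

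**Conclusion.** The point holds for LOCF. The written rule for the primary endpoint has no upper day, can select follow-up pain under either the *latest* or the *closest* reading, and contains definitions that yield different averages. A follow-up value also conflicts with the while-on-treatment description.

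For BOCF the point is narrower: no rule is given, and the formula taken literally repeats LOCF although the shells show that this is not intended.

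The effect on results is probably small. The share affected and the residual effect are assumptions, and simulated power falls below 80% (0.796) only at the 10% ceiling, with no residual effect and ED50 750. These figures do not show that the trial is underpowered, and the plan's power statement stands. The correction is worth making because it concerns the primary endpoint and is easily settled before unblinding.

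**What to change.** - **LOCF.** Define the imputed period as the last 7-day period with at least four scores that ends on or after Day 11 (14 − 3) and no later than Day 87 (84 + 3). Delete the phrases about the latest seven non-missing entries and about closeness to the nominal visit.
- **Entries after the end of treatment.** State how they are handled, in the same way for observed and imputed Week 12 values. A cap at 14 days after the last dose applied only to imputed values would not deliver a while-on-treatment endpoint, because a subject who stopped dosing early but has a valid Day 84 window would still contribute off-treatment pain.
- **BOCF.** Define a separate Week 12 BOCF variable: the baseline average carried forward, so change = 0, for mITT subjects with an evaluable baseline and no observed Week 12 average. Compute the BOCF change from it, and correct the formula in Section 6.1.8. Other BOCF conventions exist; the plan needs to fix one in writing.

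The cost is a few lines of SAP text and a short programming change. No new data are needed.

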6.1.5. Analysis Visit Windows

Statistical analyses will be based on scheduled visits and windows as per Protocol Table 2-1: Schedule of Events. If an assessment falls between 2 windows, then the closest visit will be used only if an assessment result is not provided within that window. All other visits will be listed only as unscheduled visits. For presentation purposes these will be mapped to the visit prior and labeled, e.g., Unscheduled Visit 3.1, if Visit 3 was the closest date prior.

For pain diary data the following analysis periods will be defined:

• Week X_i: the 7-day period ending within the protocol window Day Y_i±3 where at least 4 days out of 7 have recorded diary pain scores. Where several such windows exist the one ending closest to day Y_i will be selected. If there are two such windows that are equidistant from day Y_i, then the one with the largest number of diary entries will take precedence. If they have the same number of entries, then the later of the two end dates will be chosen. If no such window exists, then week X_i will be considered missing for the purposes of weekly average scoring.

Where:

• $X_1=2, Y_1=14$

• $X_2=4, Y_2=28$

• $X_3=6, Y_3=42$

AD-ST-33.06 Effective date: 12-Nov-2020

Version 1.1 | Date 31-Aug-2023 | AD-PR-109.02 Effective date: 17-Aug-2020

Page 20 of 54

- $X_4=8, Y_4=56$
- $X_5=10, Y_5=70$
- $X_6=12, Y_6=84$
- The week before follow-up is defined as the 7-day period prior to the last day of pain diary data for subjects completing the study (i.e., entering in the Week 18) where at least 4 days out of 7 have recorded diary pain scores.

6.1.6. Pooling of Sites

Analysis by investigative site will not be conducted.

6.1.7. Efficacy Variables

6.1.7.1. Pain Numerical Rating Scale

Subjects will assess their perceived average neuropathic pain over the previous 24 hours using an 11-point NRS, with 0 representing no pain and 10 representing the worst pain imaginable. Subjects will be instructed to assess their average daily pain at approximately the same time every morning, and to record their response in a subject diary (ePRO).

6.1.7.2. Neuropathic Pain Scale

Subjects will assess their neuropathic pain using the Galer NPS. The NPS includes 2 descriptors of pain, including intensity and unpleasantness, and 8 descriptors that assess specific qualities of neuropathic pain: sharp, hot, dull, cold, sensitive, itchy, deep, and surface pain. Each of these 10 dimensions has a 0 to 10 NRS in which 0 is equal to no pain and 10 equals the most intense pain. There is an additional descriptor about duration and frequency of pain, which has a 1 to 3 NRS. In which 1 = I feel a background pain all the time and occasional flare-ups (breakthrough pain) some of the time, 2 = I feel a single type of pain all the time, and 3 = I feel a single type of pain only sometimes. Other times, I am pain free.

[figure not shown]
6.1.7.3. Daily Sleep Interference Scale

Subjects will assess how their neuropathic pain interferes with their sleep using the DSIS. The DSIS is an 11-point Likert scale, with 0 indicating that pain did not interfere with sleep and 10 indicating that pain completely interfered with sleep. The DSIS is completed by subjects once a day (upon awakening) to accurately capture variability in sleep interference due to pain on a daily basis, thus minimizing recall bias.

6.1.7.4. Patient Global Impression of Change

Subjects will rate their overall improvement in health status using the PGIC. The PGIC consists of a 7-point scale where 1 = "very much improved" and 7 = "very much worse." Subjects will be asked the following question: "How would you rate your overall improvement with treatment

AD-ST-33.06 Effective date: 12-Nov-2020

during the clinical study?" The response options include the following:

- Very Much Improved 1
- Much Improved 2
- Minimally Improved 3
- No Change 4
- Minimally Worse 5
- Much Worse 6
- Very Much Worse 7

6.1.7.5. Short-Form Health Survey

The subject's health status and quality of life will be assessed using the SF-36. The SF-36 assesses 8 health concepts: 1) limitations in physical activities because of health problems; 2) limitations in social activities because of physical or emotional problems; 3) limitations in usual role activities because of physical health problems; 4) bodily pain; 5) general mental health (psychological distress and well-being); 6) limitations in usual role activities because of emotional problems; 7) vitality (energy and fatigue); and 8) general health perceptions. The items use Likert-type scales with either 5 or 6 points, or 2 or 3 points. Scores will be derived by the validated built-in scoring tool. Higher SF-36 scores indicate a better state of health.

6.1.7.6. Rescue Medication Use

Subjects will record all rescue medications they take for neuropathic pain in a paper diary. This will be transcribed in to the eCRF collecting usage, date and time of rescue medication, medication administered, dose, frequency and route.

Subjects will be grouped by the following for rescue medication use:

- Compliant with protocol guidance on permitted therapies
- Non-compliant with protocol guidance on permitted therapies

A review of medications will be conducted at a blinded data review meeting to be held before the study database is locked.

[figure not shown]

AD-ST-33.06 Effective date: 12-Nov-2020

6.1.8. Derived Variables

- Change from baseline = value at current time point value at baseline.
- Reference End Date = Date of completion/discontinuation.
- Study duration = Reference end date date of first dose of treatment + 1
- Duration of exposure (days) = min(date of last dose of treatment + 14 days or date of death) date of first dose of treatment + 1.
- Treatment-emergent AEs (TEAEs) are defined as:
 - o AEs with onset at the time of or following the start of treatment with IP, or
 - AEs starting prior to the start of treatment but increasing in severity or relationship at the time of, or following, the start of treatment with IP.
- Average Baseline Pain NRS = the arithmetic average of the 'non-missing' daily pain scores within the baseline period defined in Section 6.1.1. For example, if a subject has 5 days of non-missing pain scores their average will be calculated over 5 days, not the full 7-day baseline period.
- Average Week X Pain NRS = the arithmetic average of the 'non-missing' daily pain scores within each subject's specific week X period defined in Section 6.1.5.
- Average Week 12 Pain NRS (LOCF) = the arithmetic average of the 'non-missing' daily pain scores within each subject's specific week 12 period or according to the imputed LOCF/BOCF approach defined in Section 6.1.4.
- Change from Baseline to Week X Pain NRS = for each subject 'Average Week X Pain NRS' minus 'Average Baseline Pain NRS'.
- Change from Baseline to Week 12 Pain NRS (LOCF/BOCF) = for each subject 'Average Week 12 Pain NRS (LOCF)' minus 'Average Baseline Pain NRS'.
- Galer NPS Total Score (ranges from 0 to 100): sum of Pain Intensity, Pain Unpleasantness, Pain Sharpness, Pain Hotness, Pain Dullness, Pain Coldness, Pain Sensitivity, Pain Itching, Deep Pain Intensity, and Surface Pain Intensity (All in an 11-point NRS).
- Change from Baseline to Week X Galer NPS Total Score = for each subject 'Galer NPS Total Score' minus 'Baseline Galer NPS Total Score'.
- Total number of days rescue medication was used = End Date of Medication Start Date

of medication + 1. Each day on which rescue medication was used at least once is counted.

- Cumulative consumption (mg) of paracetamol rescue medication use = Total dose of rescue medication (mg) consumed during the days in which paracetamol was used.
- Average daily dose (mg) of paracetamol rescue medication use = Cumulative consumption of paracetamol rescue medication (mg) /total number of days paracetamol rescue medication was used.

